4.0 STAGING CRITERIA

The staging criteria for this study will be the FIGO Classification, 2003 Clinical Staging – Carcinoma of the breast. In order to be eligible for this study, patients must have been diagnosed with DCIS or invasive breast cancer on core biopsy.

5.0 ELIGIBILITY CRITERIA

Each of the criteria in the following section must be met in order for a patient to be considered eligible for registration.

- 5.1 Patients must have suspicion of DCIS or early invasive breast cancer on mammography.
- 5.2 Patients must have histologically confirmed diagnosis of DCIS or early invasive breast cancer on core biopsy for final registration.
- 5.4 Patients must be over 18 years of age
- 5.5 Patients must be postmenopausal as defined by one of the following criteria:
 - a. Prior bilateral oophorectomy OR
 - b. > 12 months since LMP with no prior hysterectomy OR
 - c. a & b not applicable AND age \geq 50
- 5.6 Patients must be positive for either ER or PR or both
- 5.7 Patients must be informed of the investigational nature of this study and must sign and give written informed consent in accordance with institutional and federal guidelines.

6. STRATIFICATION FACTORS: No stratification is planned

7.0 TREATMENT PLAN

- 7.1. Patients entered into this trial will be treated with the following regimen.
 - a. Anastrozole 1 mg by mouth for 2 - 4 weeks. The study doctor or a member of the study team will document the exact start time of treatment.
- 7.2 Good Medical Practice

The following pre-study tests should be obtained within 28 days prior to beginning treatment in accordance with good medical practice. Results of these tests do not determine eligibility and minor deviations would be acceptable if they do not impact on patient safety in the clinical judgement of the treating physician. The Study Coordinator must be contacted if there are significant deviations in the values of these tests.

WBC \geq 2,000/ μ l, ANC $>$ 1,000/ mm^3 and platelets $>$ 100,000/ mm^3 .

No serious illness or condition that would compromise ability to comply with protocol treatment and follow up.

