The successful completion of specific aims 1 and 2 will allow us to determine whether there is reduction of Ki-67 in response to 4 weeks of anastrozole and what percentage of patients show reversibility of carcinogenesis process by histopathological evaluation of lumpectomy/mastectomy specimen. Specific aim 3 and 4 will define angiogenesis response to hormonal manipulation as reflected by MRI and IHC. In this manner the best surrogate endpoint will be established to be used in future trials of hormonal agents, angiogenesis inhibitor, biological response modifiers etc. This will further allow a fast screening of chemopreventive agents by using the intermediate endpoint of breast cancer risk reduction instead of using the breast cancer risk reduction as the endpoint.

Breast cancer is one of the most common cancers seriously afflicting women in the United States. Of the one million incident cases that are reported annually there are approximately 193,000 new cases of breast cancer (Greenlee, 2001). Although significant advances have been made both in early detection and treatment of breast cancer, the impact of these on reduction in mortality has been modest (Peta, 2000). Furthermore, despite data implicating diet and other environmental risk factors, no lifestyle changes have yet been shown to significantly reduce the risk of breast cancer. Therefore, chemoprevention of breast cancer is a worthwhile approach to reduce the incidence of breast cancer.

There is every reason to believe that a detailed understanding of the initiation, promotion and growth of breast cancer will ultimately provide a rational strategy upon which to base prevention strategies. While the pathways of breast cancer development are not yet fully understood, a role for estrogens in breast cancer etiology has been well established (Hulka, 1995; Kreiger, 1999).

While many pathways are involved in breast cancer etiology, including loss of tumor suppressor function by p53 or BRCA1 and gain of HER2 oncogene expression, their exact role in an individual patient's cancer development may vary (Marquis, 1995; Boggio, 1998).

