Angiogenesis plays a fundamental role in tumor growth and metastasis. Investigations by Teruyama et al. and Mastuyugin et al. have established a relationship between VEGF expression and p450 aromatase activity (Teruyama, 2001; Mastuyugin, 2002). We have previously shown that dynamic contrast enhanced MRI in conjunction with compartmental modeling may be used to assess the angiogenic status of tumors while enabling the study of both breasts (Su, 2002). Additionally, image based measurement techniques do not suffer from the errors due to tissue heterogeneity and use of limited spatial sampling imposed in methods such as histology. Furthermore, MRI based parameters that describe breast physiology have been found to correlate well with immunohistochemically measured angiogenesis markers (Su, 1995; Su, 1994; Su, 1996). *Thus, dynamic contrast enhanced MRI will be used as a secondary surrogate marker in the proposed study.*

Methodology to test the hypothesis: Core biopsies will be obtained from patients whose mammographic findings are suspicious for DCIS. Patient will undergo MRI study prior the biopsy. At the time of biopsy, a portion of the tissue retrieved will be sent in formalin for histopathological examination for Ki-67, ER, PR and angiogenesis markers evaluation.

1 mg of anastrozole administered orally daily for 4 weeks after the diagnosis of DCIS/invasive breast cancer. The reason for using a 4-week regimen is that this is the average time between diagnostic biopsy and definitive lumpectomy or mastectomy.

Patients will undergo MRI at baseline before therapy and then again after anastrozole treatment that will be followed immediately by definitive surgical procedure, i.e. lumpectomy or mastectomy. Lumpectomy/mastectomy specimen will be again evaluated for the level of tumor

Ki-67 decline and the level of angiogenesis markers. The specimen will be subjected to the routine histopathological, and ER and PR evaluation. Histopathological changes pre and post anastrozole will be evaluated in an exploratory analysis.

Detailed Methodology

1. **Quantification of Ki-67 as a Primary Marker to Monitor Response to Chemoprevention by Aromatase Inhibitor Anastrozole**

Measurement of Ki-67 Levels.

[figure not shown]
Measurement of **Ki67** will be performed with the MIB1 mouse monoclonal antibody. To ensure acceptable precision, quantitation of Ki67 will involve the counting of 1000 cells.

Other Tissue Biomarkers.

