11.0 STATISTICAL CONSIDERATIONS

Statistical Power: In this non-randomized trial, the primary surrogate marker will be Ki-67. Individuals who exhibit at least 40% reduction in Ki-67 from baseline will be categorized as responders. For p = probability of response, the null hypothesis is specified as p_0 , and the alternative as p_1 . Our null hypothesis is that after 4 weeks of therapy, no more than 5% of the subjects will exhibit at least 40% decrease in Ki-67 levels. Table 1 gives the number of subjects necessary to detect differences of 25% to 45% from the null proportion of 5%, using the binomial test with a significance level of 0.05. Thus, for 90% power, 24 evaluable subjects are necessary to detect a difference of 25% from the null. Because of the necessity of working with patients with a small tumor size all patients accrued may not be evaluable. We anticipate a non-evaluability rate of 50% as quoted by experienced investigators. Hence, we will accrue 42 patients on this trial.

In this non-randomized trial, the primary surrogate marker will be Ki-67 level.

Table 1. Number of subjects, $p_0 = 0.05$

p_1	80% Power	90% Power
0.30	18	24
0.35	12	18
0.40	10	12
0.45	9	10
0.50	5	9

All of the quantitative results generated by IHC (percentage of eg. Ki67) will be given as their arithmetic mean levels. The comparison of changes in proliferation markers and receptor levels between responders and nonresponders will be performed using the Mann-Whitney U test.

The Primary outcome is response to treatment. For each participant, the post-treatment level of Ki-67 will be compared to the pre-treatment level of ki-67. If at least a 40%

decrease from the pretreatment level achieved, the participant will be classified as a responder. The proportion responding and the 95% confidence interval for this proportion will be calculated. The 2-sided binomial test with $\alpha = 0.05$ will be performed to test $p_0 = 0.05$ vs. $p_0 \neq 0.05$.

The secondary aims of the study are to evaluate change from baseline in the MRI parameters, vascular volume (V_b) and K_2 . The distribution in changes from baseline in tumor estrogen, V_b , and K_2 will be examined using probability plots. The Kolmogorov-Smirnov goodness-of-fit test for normality will be performed. If indicated, normalizing transformations will be applied. Ninety-five percent confidence intervals for mean change from baseline and mean percent change from baseline will be computed.

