15.0 ADVERSE EVENT REPORTING

- 15.1 An **adverse event** is defined as any untoward medical occurrence that occurs from the first dose of study medication until 30 days after the final dose, regardless of whether it is considered related to a medication.

In addition, any known untoward event that occurs subsequent to the adverse event reporting period that the investigator assesses as possibly related to the investigational medication should also be considered an adverse event.

- 15.2 A **preexisting condition** should **not** be reported as an adverse event unless the condition worsens or episodes increase in frequency during the adverse event reporting period.
- 15.3 Symptoms of the targeted cancer should not be reported as adverse events.
- 15.4 A **serious** adverse event is one that is fatal or life-threatening (i.e., results in an immediate risk of death), is permanently or substantially disabling, requires or prolongs hospitalization (only if related to an unexpected complication), or is a congenital anomaly, new cancer or medication overdose. This category also includes any other event the investigator judges to be serious or which would suggest a significant hazard, contraindication, side effect or precaution.
- 15.5 An **unexpected** event is one that is **not** listed as a known toxicity of the investigational drug in the protocol, the consent form, the package insert, or the investigator brochure.
- 15.6 **Serious, unexpected, drug-related** adverse events must be reported to the FDA and to IRB within 10 working days (report deaths within 3 days to the FDA). Please report these events to the FDA on the **MEDWATCH form** and ensure "causality" is assigned.

A cover page should accompany the Medwatch form indicating the following:

- Arimidex Investigator Sponsored Study (ISS)
- The investigator IND number assigned by the FDA
- The investigator's name and address
- The trial name and AstraZeneca Reference number

Send by way of fax to: [contact], Attention Arimidex ISS Safety Representative

If a non-serious AE becomes serious, this and other relevant follow-up information must also be provided to AstraZeneca and the FDA.

10.6.1 Address for submitting **MEDWATCH forms** to the **FDA**:

MEDWATCH
[name]
[name]
FAX #: [name]

MASTER FORMS SET

This section includes copies of all data forms which must be completed for this study. These include:

- a. Registration Form (Form #1)

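### Section 7.1 allows 2 to 4 weeks of anastrozole but the primary null hypothesis is stated for 4 weeks, and Section 11 does not say how shorter courses are counted

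*Combined protocol and SAP*

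**What the plan says.** All references are to the combined protocol and SAP.

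**Places that give a duration**
- Section 7.1, the operative treatment instruction: "Anastrozole 1 mg by mouth for 2 - 4 weeks".
- Section 2.0, summary of the specific aims: the trial is to determine "whether there is reduction of Ki-67 in response to 4 weeks of anastrozole".
- Section 2.0, methodology: "1 mg of anastrozole administered orally daily for 4 weeks after the diagnosis of DCIS/invasive breast cancer". The reason follows: "The reason for using a 4-week regimen is that this is the average time between diagnostic biopsy and definitive lumpectomy or mastectomy".
- Section 11.0, primary null hypothesis: "after 4 weeks of therapy, no more than 5% of the subjects will exhibit at least 40% decrease" in Ki-67.

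**Places that bear on the primary endpoint and give no duration**
- Objective 1.1 and Specific Aim 1, which speak of Ki-67 in treated patients, before and after treatment.
- Endpoint 10.1, which is pre versus post anastrozole.
- The Section 9.0 calendar, which puts Ki-67 on the core biopsy and after lumpectomy.
- The Section 11.0 responder rule: "For each participant, the post-treatment level of Ki-67 will be compared to the pre-treatment level of ki-67", with a fall of at least 40% making a responder.
- The Section 11.0 reporting sentence, "The proportion responding and the 95% confidence interval for this proportion will be calculated", and the statement of the two-sided binomial test against 0.05.

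The only reason Section 11.0 names for a patient not being evaluable is small tumor size. Section 6 plans no stratification.

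**The concern.** A patient can follow Section 7.1 exactly with half the exposure named in the hypothesis. If that patient has both Ki-67 samples, nothing in Section 11.0 keeps her out of the primary test or marks her as different.

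Shorter courses are foreseeable from the plan's own rationale. Four weeks was chosen as an average interval from biopsy to surgery, so unless every interval is equal, some patients reach surgery sooner. The documents do not give the spread of that interval.

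What is at stake is the meaning of the primary estimate. The hypothesis says 4 weeks, while the reporting sentence attaches no duration and no exposure summary is planned. A reader of the results would naturally take the responder proportion as a 4-week rate and could not tell whether it is one.

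**Working it through.** **1. Does the contradiction reach the primary analysis?** Take a patient given 2 weeks of drug, with a core biopsy and a surgical specimen.
- Section 7.1: compliant.
- Endpoint 10.1 and the Section 9.0 calendar: both Ki-67 values exist.
- Responder rule: she is classified, with no duration check.
- Evaluability: the one stated reason for exclusion does not concern duration.
- Null hypothesis: she lies outside its wording.

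So she is counted. This follows from the absence of an excluding rule; no sentence says that she is to be included.

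**2. The plan's own sample size.** Inputs from Section 11.0: p0 = 0.05, p1 = 0.30, two-sided alpha 0.05, 90% power, 24 evaluable. The exact binomial with at most 0.025 in the upper tail, taking the smallest n that reaches the target power, gives 18, 12, 10, 9, 5 (80%) and 21, 18, 12, 10, 9 (90%). That matches nine of the ten cells of Table 1. For the tenth, the plan states 24; the first n reaching 90% is 21, and power stays at or above 90% from n = 25. At n = 24:
- Reject at 5 or more responders (equal tails): size P(X ≥ 5 | 0.05) = 0.006; power P(X ≥ 5 | 0.30) = 0.889.
- Reject at 4 or more (minimum-likelihood two-sided p-value): size 0.030; power 0.958.

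Duration does not enter this arithmetic, so the contradiction does not make 24 wrong.

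**3. Type I error.** Let w be the share of short courses. The tested rate is

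p = w × (short-course rate) + (1 − w) × (4-week rate).

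If both null rates are 0.05, then p = 0.05w + 0.05(1 − w) = 0.05 for every w, and the size is unchanged.

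**4. Power.** It falls only if the short-course rate is below the 4-week rate. The documents give neither that rate nor w, so the table takes assumed overall rates. For example, w = 0.5 with an assumed short-course rate of 0.20 gives 0.5 × 0.20 + 0.5 × 0.30 = 0.25. The last column uses the 21 evaluable patients implied by the plan's 42 accrued at 50% non-evaluable (42 × 0.5 = 21), where both two-sided conventions reject at 4 or more.

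| Overall rate | n = 24, reject at ≥5 | n = 24, reject at ≥4 | n = 21, reject at ≥4 |
|---|---|---|---|
| 0.30 (planned) | 0.889 | 0.958 | 0.914 |
| 0.275 | 0.831 | 0.929 | 0.870 |
| 0.25 | 0.753 | 0.885 | 0.808 |
| 0.225 | 0.656 | 0.822 | 0.728 |

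If response is the same at 2 and 4 weeks, the first row applies whatever w is.

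**The case against.** The strongest reply is that this is a pre/post comparison in the window before surgery. Objective 1.1, Specific Aim 1, endpoint 10.1, the calendar and the formal test all describe it without a duration. In Section 11.0, 4 weeks appears only in the null-hypothesis sentence, and the methodology itself calls it an average. On that view, 2 to 4 weeks is practical flexibility and the 4-week phrases are shorthand.

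Part of this stands. The clash is confined to four places, and the duration-free text fits a mixed-exposure design. But the methodology presents 4 weeks as a regimen and gives a reason for it, and the hypothesis being tested names it. If the flexible reading is intended, the hypothesis and conclusion should say so.

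A reader might also infer that the trial is underpowered or the sample size wrong. The documents do not support that. The size of any loss rests on assumed values and on which rejection rule and evaluable number apply: at an overall rate of 25%, power is 0.75, 0.89 or 0.81 across the three columns above. Nor do they support a claim that the plan deliberately includes 2-week patients, since the term evaluable is never fully defined and their inclusion follows from silence.

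**Conclusion.** The contradiction is definite and reaches the primary analysis. Section 7.1 permits 2 to 4 weeks, while the aims summary, the methodology and the primary null hypothesis say 4, and no rule in Section 11.0 deals with the difference. The established consequence concerns interpretation: the primary responder rate may mix exposures and still be reported as a 4-week rate.

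No numerical harm is established. The stated 24 is unaffected. Type I error is unchanged provided the 5% null rate holds at both durations. Power could fall only if shorter exposure yields fewer responders, and by an amount that the documents do not allow anyone to calculate. They also give no basis here for saying which duration is right. The point deserves correction because it concerns what the main result means and is cheap to settle before results are seen.

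**What to change.** 1. Reconcile the aims summary and methodology in Section 2.0, Section 7.1 and the null hypothesis in Section 11.0 on treatment duration. The choice is the sponsor's.
2. Word the null hypothesis and the eventual conclusion for the exposure actually allowed.
3. Add a sentence to Section 11.0, before results are seen, stating how courses shorter than 4 weeks are counted in the primary test.
4. Report actual days on drug (median and range) beside the responder rate. Section 7.1 already has the start of treatment documented, and the adverse-event window in Section 15.1, which runs "from the first dose of study medication until 30 days after the final dose", implies a final-dose date. The contents of the data forms are not shown, so the sponsor should confirm that this date is captured.
5. In the same edit, reconcile the timing of the second MRI in Section 10.3 with the methodology in Section 2.0 and the Section 9.0 calendar. This review does not say which is right.

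The cost is wording changes, one added sentence and one line of exposure summary, with no new visit, sample or patient. The downside is that the conclusion may be less specific than 4 weeks. No breakdown of response by duration is requested, because the cells would be small with 24 evaluable patients.

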7.4 Criteria for removal from protocol treatment

- a. Progression of disease.
- b. Unacceptable toxicity
- c. Delay in treatment due to toxicity $>$ 14 days beyond scheduled treatment time.
- d. The patient may withdraw from the study at any time for any reason.
- e. Completion of treatment.

7.3. All reasons for discontinuation of treatment must be documented in the Flow sheet.

7.5 All patients will be followed until death or a maximum of 7 years.

8.0. TOXICITY TO BE MONITORED AND DOSAGE MODIFICATION

8.1 Acute morbidity potentially associated with hormonal therapy will be monitored and recorded on the Therapy and Toxicity Summary Form (Form #xxxxx) for all patients during therapy. Any chronic toxicities will be recorded on the Follow-Up Form (Form #xxxxx) at each follow-up visit. This will include hot flashes (as defined in Section 10.5), vaginitis, vaginal bleeding, tumor flare, nausea, vomiting, constipation, diarrhea, abdominal pain, xerostomia. All toxicities will be assessed based on the NCI Common Toxicity Criteria. Others include wt gain, anxiety, confusion, dizziness, insomnia, paresthesia, thromboembolism, fatigue, UTI, arthralgia and injection site reaction.

Hot Flashes: Avoid hormone treatment for hot flashes. Use hormone alternatives, example; clonidine, Beralgan, prozac or effexor while continuing with treatment protocol treatment.

8.2 Unexpected or fatal toxicities (including suspected reactions) must be reported to the to the Study Coordinator

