9.0 STUDY PARAMETERS

Test/Observation	Prior to Study	Post Anastrozole	Post Lumpectomy
History	X		
Physical Examination	X		
Mammographic findings (suspicious for DCIS or early invasive breast cancer)	X		
MRI findings	X	X	
Ki-67	X (on core biopsy)		X
Confirm DCIS or early invasive breast cancer on pathology	X (on core biopsy)		Final pathological diagnosis
Assessment of Tumor Grade and Histologic Type	X(on core biopsy)		Final pathological diagnosis
ER/PR status	X(on core biopsy)		Confirm ER/PR status
IHC scores of markers of angiogenesis	X(on core biopsy)		IHC scores of markers of angiogenesis

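### Acute, non-fatal events in the 30 days after the last dose are adverse events under 15.1, but have no clearly assigned form unless they meet the expedited criteria of 15.6

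*Combined protocol and SAP*

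**What the plan says.** Section 15.1 defines the adverse event window and its causality rule. An event counts if it "occurs from the first dose of study medication until 30 days after the final dose", and it counts "regardless of whether it is considered related to a medication".

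Section 8.1 says what goes on which form. For the short term, acute morbidity that may be linked to hormonal therapy "will be monitored and recorded on the Therapy and Toxicity Summary Form (Form #xxxxx) for all patients during therapy". For the longer term: "Any chronic toxicities will be recorded on the Follow-Up Form", at each follow-up visit. A list of toxicities comes after these two sentences. It includes short-lived symptoms such as nausea and vomiting, and also thromboembolism.

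The calendar in 9.0 ticks history and "Physical Examination" before study entry only. Its post-anastrozole column holds the MRI, and its post-lumpectomy column holds pathology and tissue markers. No row covers toxicity or adverse events. The forms list at the end of Section 15.0 names a Treatment and Toxicity Form, a Follow-Up Form (#5) and a Notice of Death (#7), but no general adverse event form.

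**The concern.** One section says what an adverse event is and another says where it is written down, and the second covers less than the first. A site that takes 8.1 and the calendar as its instructions has no clear direction to record an acute event once dosing stops, unless a narrower reporting rule applies. The Background methodology (2.0) places definitive surgery straight after treatment and the second MRI, so the weakly covered period is the perioperative month.

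The risk lies in how the record is read. Section 11.0 asks the Study Committee to monitor the data for toxicity. If some sites or staff record post-dose events and others do not, few entries could be taken for few events. The same applies on treatment to events thought unrelated to hormonal therapy: 15.1 counts them, and 8.1 does not send them to a form.

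**Working it through.** No sample size, power or alpha figure is involved. The check compares the sections and then works out the window lengths.

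**Step 1. Coverage.**

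| | 15.1 definition | 8.1 toxicity form | 8.1 Follow-Up Form |
|---|---|---|---|
| Period | First dose to 30 days after last | During therapy | Follow-up visits, none scheduled in 9.0 |
| Cause | Any | Possibly linked to hormonal therapy | Toxicities |
| Kind | Any | Acute | Chronic |

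An acute event after the last dose falls outside the toxicity form by period and outside the Follow-Up Form by kind. An event unrelated to hormonal therapy falls outside the toxicity form by cause, even during treatment.

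**Step 2. Other routes.**

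- 15.6: events that are serious, unexpected and drug-related go to the FDA and IRB, with a MedWatch form for the FDA. All three conditions must hold. There is no limit to the treatment period.
- 8.2: unexpected or fatal toxicities go to the Study Coordinator. No form is named.
- Form #7: deaths.

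What remains without a clearly assigned form is an acute, non-fatal, post-dose event that is non-serious, expected or not drug-related. An event that is unexpected but fails 15.6 on another count can still be reported under 8.2 if it is a toxicity.

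**Step 3. A worked case.** Take a non-fatal thromboembolism ten days after surgery.

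- 15.1: counts, because with surgery straight after dosing it falls within 30 days.
- 8.1 toxicity form: therapy has ended.
- 8.1 Follow-Up Form: the event is not chronic, although the list that follows names thromboembolism. The wording is ambiguous.
- 15.6: fails. Under 15.5 an event listed as a known toxicity in the protocol is not unexpected, and thromboembolism is listed in 3.0 (3.5%) and in 8.1.
- 8.2: fails, being neither unexpected nor fatal.
- Form #7: does not apply.

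**Step 4. Window lengths.** Section 7.1 gives 2 to 4 weeks of treatment, which is 14 to 28 days.

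- 15.1 window: 14 + 30 = 44 days, or 28 + 30 = 58 days.
- 8.1 acute recording: 14 days, or 28 days.
- Remainder: 44 − 14 = 30 days, or 58 − 28 = 30 days.

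These are lengths of time. They say nothing about how many events would fall in them.

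**The case against.** The strongest reply is that the sections do different jobs. Section 8.1 sets toxicity monitoring, 15.1 defines an adverse event, and nothing says that 8.1 limits Section 15. The word only does not appear in 8.1, and a site could follow both sections. This stands to a degree: the text does not forbid recording post-dose events. It still does not say where they go, because Section 15 supplies a form for the expedited events alone.

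A second reply is that the contents of the forms are unknown. The lettering of the forms list skips from c to h and from i to l, 8.1 gives placeholder form numbers, and no form is reproduced. The list in 8.1 could also be read as applying to the Follow-Up Form. This stands in full and limits the conclusion to what the text assigns.

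A third is that safety is not among the objectives in 1.0 and has no endpoint or analysis in 10.0 or 11.0. One arm with surgery planned for every patient could not separate drug effects from surgical ones. That is fair against any claim that the trial fails to show perioperative safety. It does not remove the mismatch between two stated collection rules.

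A reader might also infer that tumor flare is caught in a conflict, since 8.1 lists it and 15.3 says "Symptoms of the targeted cancer should not be reported as adverse events". The documents do not support this. Section 3.0 lists flare under human toxicity as reported during anastrozole therapy, so it is a listed drug toxicity to be recorded under 8.1. The exclusion in 15.3 does not cancel that.

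**Conclusion.** The point holds in a limited form. Sections 8.1 and 15.1 differ on period and on cause, and neither the calendar nor the forms list closes the difference. Acute, non-fatal events after the last dose have no clearly assigned form unless they meet 15.6; unexpected toxicities have a reporting route under 8.2 but no form. Events unrelated to hormonal therapy also lack a form during treatment. A stated rule under-collects against the plan's own definition, so this is more than missing detail and should be corrected.

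The affected post-dose period is 30 days. No event count can be derived from the documents. The conclusion assumes that the forms collect what 8.1 describes and that surgery closely follows the last dose, as 2.0 says.

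Three stronger readings go too far:

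- That post-dose events reach no form at all: MedWatch and Form #7 take some, and 8.2 requires some to be reported.
- That a site would necessarily return an empty post-dose record: this needs the site to disregard Section 15.
- That 30/58 = 52% or 30/44 = 68% of safety information is lost: these are shares of calendar time, and some events in that time do have a route.

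**What to change.** 1. Reconcile 8.1 with 15.1, so that the toxicity form covers all adverse events from first dose to 30 days after the final dose, whatever the suspected cause.
2. Add a toxicity row to 9.0 at the existing post-anastrozole and post-lumpectomy time points. Take the 30-day status at an existing follow-up contact or by telephone. Because 9.0 schedules no follow-up visit, state which contact is meant.

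The cost is wording in the form and the calendar, plus at most one telephone contact per patient, or 42 calls at the accrual planned in 11.0. The downside is that routine postoperative events will be recorded and must be labelled as such. No dose or treatment rule changes.
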